## 7. General Aspects for Statistical Analysis

### 7.1. General Methods

- All statistical analyses will be conducted using SAS® for Windows® Version 9.4 or higher.
- All data will be listed, and summary tables will be provided.
- In general, unscheduled visit data will be listed, but not included in the summary tables by visit. Unscheduled data will be included to identify the worst-case post-baseline for safety shift tables. Unscheduled data will be used to avoid missing data.
- Summary statistics will be presented by treatment group. For continuous variables, data will be summarized with the number of patients (N), mean, standard deviation, median, Q1, Q3, minimum, and maximum by treatment group. For categorical variables, data will be tabulated with the number and proportion of patients for each category by treatment group.
- There will be no adjustment for multiplicity, thus all p-values reported will be nominal.
- All relevant patient data will be included in listings. All patients entered into the database will be included in patient data listings. Screen failure data will be included at the end of the appropriate listings and labelled 'Screen Failures'.
- Unless otherwise specified, listings will be sorted by randomized treatment, subject number and chronologically by assessment date and time.
- Missing records will be omitted from the listings, and missing data within a record will be left blank.
- Unless otherwise specified, baseline summaries will be presented for each treatment (Placebo, Orismilast 20 mg BID, Orismilast 30 mg BID, Orismilast 40 mg BID) and for Total. Safety summaries will be presented for each treatment (Placebo, Orismilast 20 mg BID, Orismilast 30 mg BID, Orismilast 40 mg BID) and for Orismilast Total. Efficacy summaries will be presented for each treatment (Placebo, Orismilast 20 mg BID, Orismilast 30 mg BID, Orismilast 40 mg BID).

### 7.2. Key Definitions

#### Treatment period

The Treatment Period for this study is 16 weeks, from Day 1 to Week 16 (112 ± 3 days).

#### Study day

If the event date ≥ date of first dose of IP, study day = event date – date of first dose of IP + 1.

If the event date < date of first dose of IP, study day = event date – date of first dose of IP.

#### Baseline Value

Baseline value will be defined as the last non-missing value recorded prior to the first intake of study treatment.

#### Change from Baseline (CFB)

CFB = Post-baseline value – Value at baseline

This document is confidential.

### Percentage change from baseline (PCFB)

PCFB = ((Post-baseline value – Value at baseline) / Value at baseline)\*100%.

### 7.3. Missing Data

Missing data will be treated as missing, except in the following cases.

#### Efficacy

Missing data for the primary analysis of primary and secondary binary endpoints will be handled with the multiple imputation method, assuming Missing At Random (MAR) within arm.

For categorical efficacy endpoint based on a continuous variable, the multiple imputation will be first done for the continuous variable, then determine the category using the imputed values.

Secondary continuous endpoints will be analyzed based on observed data using an MMRM, thus using a modelling approach assuming MAR for missing data.

For a supportive analysis of key secondary efficacy endpoints missing data will be handled as non-response.

#### Safety

- Missing AE relationship will be imputed by 'definitely'.
- Missing AE severity will be imputed by 'Grade 3'.
- Missing or incomplete dates in safety data:

In all listings, missing or incomplete dates will be left as they have been recorded. However, for calculation / sorting / assignation based on dates, the following methods will be used:

- I. The most conservative approach will be systematically considered (i.e. if the onset date of an AE/concomitant medication is missing or incomplete, it is assumed to have occurred during the treatment period (i.e. a TEAE for AEs) except if the partial onset date indicates differently).
- II. A missing/incomplete date of medical history or disease diagnosis will be assumed to have occurred before any study treatment.

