12.9.1. Adverse Events

An AE is any untoward medical occurrence associated with the use of a drug in humans. An AE can, therefore, be any unfavorable and unintended sign, including a clinically significant abnormal laboratory finding, symptom, or disease temporally associated with the use of an investigational product, whether or not considered related causally to the investigational product (US Code of Federal Regulations [CFR] Title 21 Section 312.32[a]). Any abnormal finding that is deemed not clinically significant is not an AE.

AEs include the onset of new illness and the exacerbation of preexisting conditions. Any medical condition that is present at the time when the patient is screened should be recorded on the medical history eCRF and not reported as an AE. However, if that condition deteriorates or severity changes at any time during the study, it should be recorded as an AE.

Any AEs that occur before dosing on study Baseline will be categorized as pretreatment events. TEAEs will be defined as those AEs that occur or worsen in severity after initial dosing and up to 7 days after the last dose of study drug.

Patients will be instructed to report AEs at each study visit. All AEs are to be followed up until resolution or a stable clinical endpoint is reached.

Each AE is to be documented on the eCRF with reference to date of onset, duration, frequency, severity, relationship to study drug, action taken with study drug, treatment of event, and outcome. Furthermore, each AE is to be classified as being serious or nonserious. Changes in AEs and resolution dates are to be documented on the eCRF.

For the purposes of this study, the period of observation for collection of AEs extends from the time the patient gives informed consent until the Follow-up visit. Follow up of the AE, even after the date of therapy discontinuation, is required if the AE persists until the event resolves or stabilizes at a level acceptable to the Investigator.

When changes in the intensity of an AE occur more frequently than once a day, the maximum intensity for the event should be noted. If the intensity category changes over a number of days, then those changes should be recorded separately (with distinct onset dates).

Specific guidelines for classifying AEs by intensity and relationship to study drug are given in Table 6 and Abbreviations: ADL, Activities of Daily Living; AE, adverse event

Table 7.

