## **8.6. Medication**

The WHO Drug, March 2021, B3 will be used to classify prior and concomitant medications by therapeutic class and drug name.

Prior medication is defined as any medication taken before the date of the first dose of study treatment. Concomitant medication is defined as any medication taken on or after the date of the first dose of study treatment.

The use of prior medications, concomitant medications and concomitant disallowed medications will be summarized by the number and percentage of patients for the ITT population. If a patient takes a specific medication multiple times or takes multiple medications within a specific therapeutic class, that patient would be counted only once for the coded drug name or therapeutic class.

Prior and concomitant medications will be listed for all patients in the randomized population.

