### 12.1. Adverse Events

AEs for all patients in the safety population will be included in the AE summaries.

Adverse events will be summarized by system organ class (SOC) and preferred term (PT) for each treatment and Orismilast total, based on the MedDRA dictionary version 24.0. Severity of AEs will be graded according to National Cancer Institute (NCI) Common Terminology Criteria for Adverse Events (CTCAE) version 5.

Any AEs that occur before dosing on study Baseline will be categorized as pretreatment events. TEAEs will be defined as those AEs that occur or worsen in severity after initial dosing and up to 7 days after the last dose of study drug.

Duration will be calculated for AEs that resolve as the difference between the resolution date and onset date plus 1 and expressed in days.

The summary tables will include the number of patients and the number of events. Percentages will be based on the number of patients in the safety population. For summaries by SOC and PT, a patient will be counted once at the SOC level and once at each PT within the SOC level.

For summaries by SOC, PT, and maximum severity, a patient will be counted once at the highest severity level for which the event occurred at the SOC level and the highest severity level for each unique PT within that SOC level. Therefore, patients may only contribute once to each PT and once to each SOC level.

The summaries presenting frequency of AEs by SOC and PT will be ordered by Orismilast total descending frequency of SOC and then, within a SOC, by Orismilast total descending frequency of PT.

The following tables will be provided:

- An overall summary of the number of events and number and percentage of patients reporting TEAEs, related TEAEs (TEAEs recorded as “Relationship to study drug” = “Possibly” or “Probably” or “Definitely”), serious TEAEs (TESAEs), TEAEs resulting in death, TEAEs of special interest, TEAEs leading to study drug discontinuation, TESAEs leading to study drug discontinuation, TEAEs by relationship and TEAEs by toxicity grade;
- TEAEs overall by system organ class and preferred term;

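### The SAP's missing-date rule checks only the onset date, so an AE known to have ended before the first dose can be classed as a TEAE

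*SAP*

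**What the plan says.** SAP Section 7.3 (Missing Data, Safety) opens its date rules with a principle: "The most conservative approach will be systematically considered". Rule I applies it. The trigger is "if the onset date of an AE/concomitant medication is missing or incomplete", and the consequence is that "it is assumed to have occurred during the treatment period (i.e. a TEAE for AEs) except if the partial onset date indicates differently". That exception is the only one. Neither Section 7.3 nor any other part of the SAP uses the end date for this classification.

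SAP Section 12.1 defines the categories that the rule feeds: "Any AEs that occur before dosing on study Baseline will be categorized as pretreatment events", and "TEAEs will be defined as those AEs that occur or worsen in severity after initial dosing", with an upper limit of 7 days after the last dose.

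The Protocol (12.9.1) shows that such records can exist and that the information needed to sort them is held. AEs are gathered before dosing, because "the period of observation for collection of AEs extends from the time the patient gives informed consent until the Follow-up visit". End dates are captured: "Changes in AEs and resolution dates are to be documented on the eCRF".

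**The concern.** A conservative date rule should settle real doubt in favour of the TEAE category. Where the resolution date is known and precedes the first dose, there is no doubt on the point that matters: whatever its onset, the event was over before treatment. Rule I still assigns it to the treatment period unless the onset fragment alone rules that out. A recorded fact is then overridden by an assumption, and the result contradicts the definitions in Section 12.1.

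What is at stake is the content of the TEAE summaries. Events that cannot have been caused or worsened by study drug would be tabulated as treatment-emergent. Section 7.3 also fills a missing relationship with the strongest category and a missing severity with Grade 3. A pretreatment record that lacked those fields too would appear as a related, severe TEAE.

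**Working it through.** The plan states no figure on this point, so there is none to reproduce. The check applies rule I literally to AEs whose recorded end date is before the first dose.

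**Inputs**
- Rule and its one exception: SAP 7.3.
- Definitions of pretreatment event and TEAE: SAP 12.1.
- AE collection from consent, and recording of resolution dates: Protocol 12.9.1.
- Screening visit up to 28 days before Baseline: SAP 4.1.

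**Step 1. What the rule does, by how much of the onset is known (event ended before the first dose)**

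| Known part of onset | Rule I | Section 12.1 |
|---|---|---|
| Nothing | TEAE | Pretreatment |
| Year only, same year as first dose | TEAE | Pretreatment |
| Month and year, same month as first dose | TEAE | Pretreatment |
| Year only, earlier year | Not a TEAE | Pretreatment |
| Month and year, earlier month | Not a TEAE | Pretreatment |

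The sections conflict in the first three rows and agree in the last two.

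**Step 2. One record.** Onset 'Mar 2022', resolved 10 March, first dose 15 March. March 2022 includes days on and after 15 March, so the onset fragment does not trigger the exception and the event is a TEAE. It ended 15 − 10 = 5 days before dosing.

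**Step 3. How often the exception rescues a record (illustration only).** Assumptions, not from the documents: first dose equally likely on any day of 2022; onset 1 to 28 days before the first dose; end on any day from onset to the day before dosing; all combinations weighted equally.
- Combinations per first-dose day: 1 + 2 + … + 28 = 28 × 29 / 2 = 406. Over the year: 365 × 406 = 148,190.
- Onset wholly missing: all are TEAEs, 100%.
- Year only: the exception works only when onset falls in 2021. With T(n) = n(n + 1)/2, the number rescued is the sum over n = 0 to 28 of 406 − T(n) = 29 × 406 − 4,060 = 7,714. Share classed as TEAE: 1 − 7,714 / 148,190 = 94.8%, about 95%.
- Month and year: a TEAE results only when onset falls in the dosing month. The count is 4,872 for each of seven 31-day months, 4,466 for each of four 30-day months and 3,654 for February: 34,104 + 17,864 + 3,654 = 55,622. Share: 55,622 / 148,190 = 37.5%, about 38%.

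These are shares of AEs that already have an incomplete onset and a pre-dose end date. They are not shares of all AEs.

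**Step 4. The rule with an end-date check.** If an end date before the first dose makes the event pretreatment, all three shares fall to 0%. For a first dose on 10 July 2022 and an end date of 5 July 2022, onsets recorded as missing, '2022' and 'Jul 2022' change from TEAE to not TEAE. Onsets recorded as 'Jun 2022' and '2021' were not TEAEs before and do not change.

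**The case against.** The strongest defence is that the rule is openly conservative, applies alike to every arm, and feeds summaries for which SAP Section 12 plans no inference. The records affected are also few. Protocol 12.9.1 requires an onset date for each AE and sends conditions present at screening to medical history. What remains is a short event within the pre-dose window with a known end and an uninformative onset. Queries are to be largely resolved before the blinded data review (SAP 6.5), which gives a chance to complete such dates. Finally, a sensible programmer might let Section 12.1 govern whenever the end date settles the timing.

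Most of this stands as a limit on size. It does not remove the contradiction. Section 7.3 gives an explicit rule with a single exception, and Section 12.1 does not say that it takes precedence when the onset is missing. Two programmers could follow the SAP and produce different TEAE counts.

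Stronger readings are tempting, but the documents do not support them:

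- *Every incomplete onset date produces the error.* It does not. An onset fragment wholly before the first dose is excluded by the rule's own exception (last two rows of the table).
- *Washed-out psoriasis drugs with an unknown start would be tabulated as concomitant disallowed medication and create false deviations.* Rule I names concomitant medication only, and SAP 8.6 says: "Concomitant medication is defined as any medication taken on or after the date of the first dose of study treatment". A drug with an earlier stop date falls outside that definition. Section 7.3 also keeps dates in listings as recorded, and per-protocol exclusions are decided at the blinded review from listings (SAP 6.5), where the stop date would be visible.
- *Safety differences between arms are diluted, or a known number of patients is affected.* The documents give no frequency of incomplete dates and nothing that shows a differential effect.

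**Conclusion.** Wrong as written, minor. Taken literally, SAP 7.3 classes an AE with a recorded pre-dose resolution as a TEAE when its onset is wholly missing, or is incomplete and does not itself show a pre-dose onset. That contradicts SAP 12.1.

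The conclusion rests on a literal reading of rule I and on the end date being known well enough to place it before the first dose. The number of such records cannot be derived from the documents; my judgement is a few events at most. The 100%, about 95% and about 38% shares describe only how often the rule misfires once such a record exists, under the stated weighting. The consequence is confined to descriptive TEAE tables. The primary and secondary efficacy analyses are untouched.

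**What to change.** Reword rule I in SAP 7.3 along these lines: *An AE with a missing or incomplete onset date is counted as a TEAE unless the known part of its onset date, or its complete or partial end date, shows that it started or ended before the date of first dose. An AE shown to have ended before that date is a pretreatment event.*

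For consistency, add that a medication whose stop date is before the first dose is prior only, which SAP 8.6 already implies.

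The cost is one clause, one clarifying sentence and one condition in the program, using resolution dates already collected. No true TEAE is lost, because an event that ended before dosing can neither begin nor worsen after it. The check should require an end date strictly earlier than the date of first dose, so that an event ending on the dosing day stays under the conservative default.

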### 7.4. Visit Windows

If there are multiple planned assessments for any study procedure at a given time point, the latest non-missing value will be used for summarization. Unscheduled assessments will be listed and will be used to flag baseline visit if this is the last non-missing assessment before the first dose of study drug, but unscheduled assessments will not be included in the summarization, unless to be used to avoid missing data at Week 4, 8, 12, 16 and 20.

Visits in RAVE captured as 'Week 16 / EoT and 'Week 20 / Follow-up' will be reassigned to either 'Week 16' or another scheduled post-baseline visit or 'EoT' and 'Week 20' or 'Follow-up' as follows: If a patient completed the study treatment (based on the End-of-Treatment form information), data captured in RAVE as 'Week 16 / EoT', will be presented as 'Week 16' irrespectively of violation of visit window. If a patient discontinued the study treatment, provided that no data are available from a certain scheduled post-baseline visit (Week 4, 8, 12, 16) for a subject, data captured on the 'Week 16 / EoT' visit have the potential to be assigned to a particular scheduled visit in data summaries and analyses, provided the data are collected between 13 days before and 14 days after the planned time point for the scheduled visit, as displayed in table below:

This document is confidential.

Visit (target day)	Visit window (day is date of assessment minus date of first dose)
Week 4 (day 28)	Day 15 to 42
Week 8 (day 56)	Day 43 to 70
Week 12 (day 84)	Day 71 to 98
Week 16 (day 112)	Day 99 to Day 139 *

\* Week 16 uses a broader visit window.

If the 'Week16/EoT' visit falls outside the visit schedule in the trial procedure it will be present as 'EoT'.

If the subject completed study treatment, data captured in RAVE as 'Week 20 / Follow-up' will be presented as 'Week 20' irrespectively of violation of visit window. If the subject did not complete study treatment, data captured in RAVE as 'Week 20 / Follow-up' will be presented as 'Follow-up'.

#### **7.5. Pooling of Centers**

Not Applicable since no adjustment for center or by center analyses are planned.

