#### **4.4. Treatment Assignment and Blinding**

Randomization will occur prior to first study treatment administration, at the Baseline visit. Patients will be assigned randomly in a 1:1:1:1 ratio to 1 of 3 orismilast dose groups (20 mg, 30 mg, or 40 mg) or placebo. The randomization is stratified by site.

A randomization list will be used to assign the treatments to each patient. The randomization list will be kept secured with access restricted to only the designated personnel directly responsible for labeling and handling the study drug until the study blind is broken at the end of study (database lock).

To facilitate the double blind, the tablets will be packaged in the same type of blister and the active and placebo tablets will have the same appearance (in terms of size, form, weight, and color). One dose consists of 2 identical tablets (a 10 mg or 30 mg orismilast tablet or a matching placebo).

This document is confidential.

Blinding codes should only be broken in emergency situations for reasons of patient safety. The patient for whom the blind has been broken will be discontinued from the study and undergo the early termination procedures. The primary reason for discontinuation (the event or condition which led to the unblinding) will be recorded.

All patients will be centrally assigned to randomized study treatment using an Interactive Web Response System (IWRS).

Sponsor safety staff may unblind the study drug assignment for any patient with a serious adverse event (SAE). If the SAE requires that an expedited regulatory report be sent to one or more regulatory agencies, a copy of the report, identifying the patient's study drug assignment, may be sent to investigators in accordance with local regulations and/or sponsor policy.

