## 9. Efficacy

For inferential analyses of primary and secondary efficacy endpoints, each active treatment group will be compared with the placebo group.

Primary and secondary efficacy endpoints are to be assessed in the ITT Population. Missing data for the primary analysis of primary and secondary binary endpoints will be handled with the following multiple imputation method: Intermittent missing data will first be imputed using the MCMC method implemented with the SAS MI procedure, which is appropriate for non-monotonic missing data. Data missing after patients discontinue treatment early will then be multiply imputed with the SAS MI procedure using a regression statement (number of imputations: 50, seed: 5863781). At each time point, missing data will be assumed to be MAR and to follow a distribution similar to scores for patients who are still in the study and randomized to the same treatment group.

For categorical efficacy endpoints based on a continuous variable, the multiple imputation will be first done for the continuous variable, then determine the category using the imputed values. Efficacy analyses will be repeated on the PP Population for primary and secondary endpoints.

When appropriate, the raw parameter, its change from Baseline, and percentage change from Baseline will be summarized.

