### 9.1. Primary Efficacy Endpoint and Analysis

The primary endpoint in this study is the percentage change in PASI score from Baseline at Week 16.

The primary endpoint (primary analysis) will be analyzed using analysis of covariance (ANCOVA) with treatment group as factor and Baseline PASI as covariate. Each active treatment dose will be compared with placebo. No adjustment for multiplicity will be made and the 0.05 level of significance will be used to claim efficacy compared with placebo. Least square means and the 95% confidence interval of the difference between each active treatment and placebo will be calculated.

The primary analysis set will be the ITT population with multiple imputation approach to handle missing values. The same analyses will be repeated for Weeks 20, 12, 8 and 4. These analyses will be repeated on the PP population.

LSMean (+/-SE) percentage change of PASI score will be presented graphically over time from Baseline to Week 4, 8, 12, 16 and 20.

Actual values, change from baseline values and percentage change from baseline of PASI will be summarized by visit using descriptive statistics and presented graphically over time.

The mixed model for repeated measures (MMRM) will be used as a supportive analysis. To ensure that all patients are included in the analysis, the baseline value for patients with no post-baseline data should be carried forward as the first post-baseline assessment, corresponding to imputing a change of 0 at the first post-baseline assessment. The MMRM model will be implemented using SAS PROC MIXED with treatment group, visit and treatment-by-visit interaction as factors and baseline PASI score by-visit interaction as a covariate. A restricted maximum likelihood (REML) will be used. The Kenward-Roger approximation will be used to estimate the denominator degrees of freedom and adjust standard errors. Least Squares Means Estimates and 95% confidence intervals will be given for each treatment group and for the difference between treatment groups (here also p-values will be presented).

This document is confidential.

PASI (including change from baseline values, percentage change from baseline values, PASI50, PASI75, and PASI90) will be listed.

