## **9.2. Secondary Efficacy Endpoints and Analyses**

Continuous secondary efficacy endpoints will be analyzed based on observed data using MMRM, using a modelling approach assuming MAR for missing data. These analyses will be repeated on the PP population.

The binary secondary efficacy endpoints will be analyzed using differences in proportions, comparing each active treatment group to placebo in the ITT population with handling of missing data as specified in Section 9. Response by treatment group and difference in response rate and p-values compared to placebo will be presented.

The secondary endpoints and the percentage change of BSA will be presented graphically over time from Baseline to Week 20. In addition, shift tables will be provided between Baseline and each visit for the IGA distribution. The PASI percentage changes from Baseline will be plotted to identify where the best separation between treatments occur. These figures and tables are based on observed cases, thus purely descriptive.

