**This document is confidential.**

- Patients achieving 50% reduction in PASI (PASI50) and 90% reduction in PASI (PASI90) response at Weeks 4, 8, 12, 16, and 20.
- Change from Baseline in PASI at Weeks 4, 8, 12, and 20.
- Change from Baseline in total Psoriasis Symptoms Scale (PSS) score at Weeks 4, 8, 12, 16, and 20.
- Change from Baseline in each individual item of the PSS at Weeks 4, 8, 12, 16, and 20.
- Change from Baseline in the affected body surface area (BSA) at Weeks 4, 8, 12, 16, and 20.
- Change from Baseline in Dermatology Life Quality Index (DLQI) score at Weeks 16 and 20.
- Patients experiencing psoriasis rebound by Week 20, defined as PASI  $\geq$ 125% of Baseline or new generalized pustular, erythrodermic, or more inflammatory psoriasis.

PASI50 represents the percentage of patients who have achieved a 50% or more reduction in their PASI score from baseline. PASI90 represents the percentage of patients who have achieved a 90% or more reduction in their PASI score from baseline.

Continuous secondary efficacy endpoints will be analyzed using MMRM, similar to the supportive MMRM for the primary endpoint. The same analyses will be repeated on the PP population.

The analysis on categorical secondary efficacy endpoints will be performed using differences in proportions, comparing each active treatment group to placebo in the ITT population with handling of missing data as specified in Section 9. Response by treatment group and difference in response rate and p-values compared to placebo will be presented.

Actual values and change from baseline values of PSS will be summarized by visit using descriptive statistics and presented graphically over time. Actual values, change from baseline values and percentage change from baseline of BSA and DLQI will be summarized by visit using descriptive statistics and presented graphically over time. The percentage of patients with PASI50 and PASI90 will be presented graphically over time. These tables and figures are based on observed cases, thus purely descriptive.

PSS (including change from baseline values) will be listed. BSA and DLQI (including change from baseline and percentage change from baseline values) will be listed.

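### Randomisation is stratified by site but the primary ANCOVA and the MMRMs omit site, so if sites differ the reported standard errors are too large and some power is lost

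*SAP*

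**What the plan says.** - Randomisation (SAP 4.4): "The randomization is stratified by site". The randomisation section of the protocol (9.2.1) does not mention this; only the SAP does.
- Centres (SAP 7.5): "Not Applicable since no adjustment for center or by center analyses are planned". No reason is given.
- Primary analysis (SAP 9.1): "analysis of covariance (ANCOVA) with treatment group as factor and Baseline PASI as covariate". Protocol 15.3.1 has the same model.
- Supportive MMRM (SAP 9.1): "SAS PROC MIXED with treatment group, visit and treatment-by-visit interaction as factors and baseline PASI score by-visit interaction as a covariate". For this model, "The Kenward-Roger approximation will be used to estimate the denominator degrees of freedom and adjust standard errors".
- Continuous secondary endpoints (SAP 9.2): "Continuous secondary efficacy endpoints will be analyzed based on observed data using MMRM". SAP 9.2.2 repeats the link to the primary MMRM: "Continuous secondary efficacy endpoints will be analyzed using MMRM, similar to the supportive MMRM for the primary endpoint".

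None of these continuous-endpoint models has a term for site or country.

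**The concern.** Blocking within site keeps the arms close to balanced at each site, so differences between sites largely cancel out of each dose-versus-placebo contrast. The estimate therefore varies less from trial to trial than it would under unstratified allocation. A model that omits site does not credit this: it counts the between-site variance as residual error and reports a standard error larger than the true one.

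The error is in the safe direction. There is no bias and no inflation of type I error, and if sites do not differ nothing changes. What is lost is the benefit in the reported intervals and tests. The dose-versus-placebo differences inform the choice of the Phase 3 dose, which is the secondary objective, and they rest on about 50 patients per arm.

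Differences between about 40 sites in four countries are possible for an investigator-scored index. Protocol 11 limits them by requiring certified assessors and one assessor per patient.

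**Working it through.** **Inputs from the documents.** Means −32.2 and −50.9, so the difference is 18.7; SD 33; 50 per arm; two-sided 5% (SAP 4.3). Four arms, 1:1:1:1, stratified by site (SAP 4.4). About 40 sites (SAP 4.1), so 200/40 = 5 patients per site.

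**Assumed, not in the documents.** Site ICC (the share of outcome variance lying between sites), shown over 0 to 0.20; block size; distribution of site sizes.

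**Step 1: the plan's own figure.** SE = 33 × √(2/50) = 6.60. Noncentrality = 18.7/6.60 = 2.83. The noncentral t on 98 df gives power 80.1%, so the stated 80% reproduces.

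**Step 2: ideal case, perfect balance within site.** True SE = 6.60 × √(1 − ICC), while the model without site reports 6.60.
- Size without site = 2[1 − Φ(1.972 × 6.60/true SE)], where 1.972 is the t quantile on 195 df.
- Power without site = Φ[(18.7 − 1.972 × 6.60)/true SE].
- Power with site: noncentral t with noncentrality 18.7/true SE, on 195 − 39 = 156 df.

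| ICC | True SE | Reported/true | Size without site | Power without site | Power with site |
|---|---|---|---|---|---|
| 0.05 | 6.43 | 1.026 | 4.3% | 81.2% | 82.4% |
| 0.10 | 6.26 | 1.054 | 3.8% | 81.8% | 84.3% |
| 0.20 | 5.90 | 1.118 | 2.8% | 83.2% | 88.3% |

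**Step 3: realistic imbalance, complete data.** Simulation of 200 patients at 40 uneven sites (gamma weights), blocks of 4, baseline covariate, 40,000 trials per ICC, averaged over the three doses. The comparison model is a random site intercept fitted by REML with Kenward-Roger.

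| ICC | True SE, no site | Reported SE, no site | Ratio | Size, no site | Power, no site | Power, random site | Half-width, no site | Half-width, random site |
|---|---|---|---|---|---|---|---|---|
| 0 | 6.64 | 6.62 | 0.997 | 5.1% | 79.9% | 80.2% | 13.04 | 12.97 |
| 0.05 | 6.48 | 6.62 | 1.022 | 4.5% | 80.5% | 81.7% | 13.04 | 12.75 |
| 0.10 | 6.35 | 6.62 | 1.042 | 4.2% | 81.3% | 83.6% | 13.03 | 12.47 |
| 0.20 | 6.07 | 6.61 | 1.089 | 3.4% | 82.3% | 87.2% | 13.01 | 11.81 |

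With blocks of 8 the gains are +0.2, +1.0, +1.9 and +4.6 points. A separate simulation with 40 equal sites of 5 agrees: at ICC 0.10 size without site is 3.8% and power goes from 80.9% to 83.7%; at ICC 0.20, 3.0% and 84.6% to 89.1%.

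About 39 fixed site effects in the Step 3 design give power 76.8, 79.4, 81.3 and 85.9%. That is below the model without site at ICC 0 and 0.05, so the form of adjustment matters.

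**Step 4: multiple imputation as planned.** 50 imputations within arm without site, with 20% of Week 16 values missing (assumed), 4,000 trials per ICC. Power is 73.4, 73.9, 74.1 and 75.2% without site and 73.7, 75.0, 76.2 and 79.8% with it, gains of 0.3, 1.1, 2.1 and 4.6 points. The level is below 80% because of the missing data, not because site is omitted. Size is 4.6, 4.2, 3.8 and 3.2% without site and 4.7, 4.6, 4.3 and 4.2% with it.

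**Step 5: MMRM at Week 16.** Observed data, same dropout, 2,000 trials per ICC. SAP 9.1 names no covariance structure, so unstructured was assumed.
- Site effect constant over visits: power 75.4, 77.1, 74.7 and 76.7% without site, against 75.6, 78.1, 77.2 and 82.4% with it.
- Site effect growing and drifting over visits: gains of only 0.1, 0.1, 0.5 and 1.3 points.

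**Step 6: binary endpoints.** For the PASI75 difference in proportions, reported/true SE is 0.988, 0.996, 1.001 and 1.018. There is no material effect, so these analyses are outside this point.

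**The case against.** The strongest reply is that this is an open, prespecified choice and not a gap. SAP 7.5 states it and Protocol 15.3.1 has the same ANCOVA. With about 5 patients per site over four arms, leaving site out is defensible, and fixed site effects can cost power. That stands against fixed effects, but not against a random intercept, which loses essentially nothing at ICC 0.

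The size also rests on an ICC that no document supplies. At 0.05 the gain is 1.2 points and about 2% of interval width; only the top of the range gives nearly 5 points. With complete data the planned power is met without site, and SAP 7.1 calls all p-values nominal. This stands, and it keeps the point small.

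The stratified design already gives the estimate its precision. Dividing the with-site half-widths by 1.972 gives 6.58, 6.47, 6.32 and 5.99, close to the true SEs without site (6.64, 6.48, 6.35, 6.07). This is correct: what is forgone is reported interval width and power, not accuracy of the estimate.

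The MMRM case is thinner. Only percentage change in PASI was simulated, not BSA, PSS or DLQI, and the gain nearly disappears if site effects drift. Under imputation the adjusted ANCOVA also stays slightly conservative. Both limits stand; neither makes the adjustment harmful.

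**Conclusion.** The concern holds as a modest, conditional improvement. The trial randomises by site and then analyses every continuous endpoint as if it had not. If sites differ, the reported SE of the primary contrasts is too large by about 2% at ICC 0.05, 4% at 0.10 and 9% at 0.20, and a random site intercept recovers about 1, 2 and 5 points of power. If sites do not differ, nothing is lost by the current plan.

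The direction follows from the design and is certain. The size depends on assumptions the documents do not settle: the ICC, the block size, the spread of site sizes and, for Steps 4 and 5, 20% missing data. Validity is not threatened, and the sample size calculation is unaffected.

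**What to change.** Amend SAP 7.5, SAP 9.1 and the MMRM text in SAP 9.2 before unblinding.

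1. **Primary ANCOVA.** Add site as a random intercept, not about 40 fixed effects, with the Kenward-Roger method already named for the MMRM. Fit it in each of the 50 imputed datasets and combine as planned. Leave the imputation model alone: it works within arm, where there are only about 50/40 = 1.25 patients per site.
2. **Zero site variance.** Keep that fit. It equals the planned model and is not a convergence failure. The rule is needed: in Step 4 the variance was zero in some but not all of the 50 datasets in 79, 57, 29 and 4% of trials.
3. **Non-convergence in any imputed dataset.** Use country (Germany, Poland, UK, US) as a fixed factor in all 50. This fallback was not simulated.
4. **MMRMs.** Add the same random intercept. If a model does not converge, use the currently planned MMRM for that endpoint. None of the 16,000 simulated fits failed, under an unstructured covariance.
5. **Binary endpoints.** Leave as planned.
6. **SAP 14.** List the departure from Protocol 15.3.1.

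The cost is SAP wording, one random term and slightly more programming. On complete data the ANCOVA test size is 5.24% at ICC 0 (5.09% without site) and 4.95 to 5.15% at ICC 0.05 to 0.20. If the sponsor prefers to keep the primary model, a prespecified sensitivity analysis with random site, plus a stated reason in SAP 7.5, would be a lesser alternative.
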